## 4. Study procedures and assessments

This study is an investigator initiated, single-center, prospective, randomized, open-label, parallel design study.

Study flow chart consists of

1. Screening visit, signing of the informed consent and randomization
2. Baseline study visit in the Obesity Research Unit with study measurements detailed below in section "Study procedures in Obesity Research Unit".
3. Baseline visit in Meilahti hospital, where MR imaging and spectroscopy, and transient elastography will be done.
4. Visit at the Infectious Diseases Clinic, where the current ART will be continued or modified according to the randomization. Patient follow up will take place according to the standard of care with two safety laboratory tests at weeks 2 and 8.
5. 24 week study visit in the Obesity Research Unit with the same study measurements as detailed at the baseline (see section below).
6. 24 week study visit in Meilahti hospital, where MR imaging and spectroscopy, and transient elastography will be repeated.
7. End of study visit (24 weeks after study start) at the Infectious Diseases Clinic, where current ART can be continued or modified according to the standard of care.

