**Exclusion criteria are:**

- Within 12 month window period prior to screening, HIV VL measurement of  $\geq 50$  cop/ml.
- More than one consecutive HIV VL measurements of  $\geq 50$  cop/ml in the treatment history after initial viral suppression with ART.
- Chronic hepatitis B or C.
- Daily alcohol consumption  $\geq 30 \text{ g}$  for men and  $\geq 20 \text{ g}$  for women.
- Pregnancy or planned pregnancy during the study period.

- Lipid or glucose lowering regimen or hormonal supplement started within 3 months before the planned study start.
- Psychiatric disorder, which prevents a study subject to understand the study protocol.
- Other serious disease, which prevents a study subject to participate in the study.
- For MRI/spectroscopy imaging: metal objects in the body or claustrophobia.

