### 4.1. Screening visit

A screening visit will be performed prior to first study visit in Obesity Research Unit. The screening visit consists of the following procedures:

- A physical examination will be performed and demographic data will be recorded including subject's gender, date of birth, ethnicity, substance use, recent and current alcohol use (AUDIT questionnaire), smoking status, weight, height, BMI, and waist and hip circumferences.
- Medical history and current medical conditions and concomitant treatments will be inquired and recorded.
- Blood pressure and heart rate will be measured.

The subject may enter into the study if all the inclusion criteria and none of the exclusion criteria are met and will be randomized to one of the treatment arms after signing the informed consent (IC). Recording of adverse events (AEs) starts from the time that a study subject signs the IC form. The study subjects will be given a study diary, where they can fill in AEs and possible concomitant treatments during the study. They will be asked to fill a dietary and exercise diary for three days at the study start and at the end of study.

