#### 4.2. Clinical follow up visits in Infectious Diseases Clinic (Aurora hospital)

Table 1 lists all study procedures in Aurora hospital, Helsinki.

Clinical follow up	Lab measurements	Other
first visit, day 1	HIV viral load, complete blood count, Creatinine, ALT, AST, CD4 count	According to the randomization, switching of a PI or efavirenz to raltegravir, or continuing with the previous ART.
remote contact by phone 1, week 2	complete blood count, CRP, ALT, Glucose, Creatinine	AEs inquired and reported
remote contact by phone 2, week 8	complete blood count, ALT, AST, Creatinine, HIV viral load	AEs inquired and reported
last visit, week 24	HIV viral load, complete blood count, Creatinine, ALT, AST, CD4 count	AEs inquired and reported

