#### 4.3. Study procedures in the Obesity Research Unit and in the Radiology Department

The study protocol includes two visits in the Obesity Research Unit. The first visit will take place after randomization and before the switch of the ART. The second visit will take place after 24 weeks of follow up.

Study subjects are advised to fast 10-12 hours before each visit in the Obesity Research Unit (water is allowed during fasting). Alcohol intake is prohibited from 48 h before each study visit. Smoking is prohibited during the visits. Apart from these restrictions the subjects are advised to keep to their usual exercise and lifestyle habits for the duration of the study.

The visits consist of the following study measurements: Oral glucose tolerance test (OGTT), measurements of liver fat by 1H-spectroscopy, body composition by MRI, hepatic stiffness by transient elastography and calorimetry for measurement of basal metabolic rate. Samples of blood, urine, stool and saliva are collected, ECG and subcutaneous adipose tissue biopsies taken, and health questionnaire filled in.

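### Randomisation takes place at screening, before the baseline measurements and the pregnancy test, in an open-label trial with no stated rule withholding the arm until day 1

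*Combined protocol and SAP*

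**What the plan says.** The flow chart in section 4 starts with "Screening visit, signing of the informed consent and randomization". Step 2 is the baseline visit to the Obesity Research Unit. Step 3 is the "Baseline visit in Meilahti hospital, where MR imaging and spectroscopy, and transient elastography will be done". The allocation is first acted on at step 4: "Visit at the Infectious Diseases Clinic, where the current ART will be continued or modified according to the randomization". Table 1 in section 4.2 dates that to day 1: "According to the randomization, switching of a PI or efavirenz to raltegravir, or continuing with the previous ART".

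Section 4.3 gives the same order for the Obesity Research Unit: "The first visit will take place after randomization and before the switch of the ART". Section 4.1 also describes randomisation under the screening visit and sets a condition: "The subject may enter into the study if all the inclusion criteria and none of the exclusion criteria are met".

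One exclusion criterion in section 3 is "Pregnancy or planned pregnancy during the study period". Section 5.3 places the pregnancy test at the first Obesity Research Unit visit, and the urine paragraph of section 4.3 places it on a study morning. The list of screening procedures in section 4.1 has no pregnancy test. Claustrophobia is a further exclusion, for the imaging.

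Section 4 describes the trial as open-label. Section 3 stratifies randomisation by age, sex and current regimen (PI or efavirenz).

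**The concern.** In an open-label trial, randomisation is best done as late as possible before treatment starts, after baseline data are collected and eligibility is settled. Here it comes first, which creates two separate problems.

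The first is knowledge of the arm. If subjects learn their allocation at screening, some may change their habits or withdraw before baseline, and not equally in the two arms. An elastography operator who knows the arm could also be influenced, and the available text does not keep the operator unaware of it. The diet and exercise record is not a safe reference: "They will be asked to fill a dietary and exercise diary for three days at the study start and at the end of study" does not say that the first diary is completed before randomisation.

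The second problem exists whether or not the arm is disclosed. A subject can be randomised before an exclusion criterion has been tested, or before it is known that a scan can be obtained. The primary objective is change in liver fat from baseline to week 24, so a randomised subject with no baseline scan cannot contribute a change score. Section 6 does not say how such a subject is handled.

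**Working it through.** **Order of events** (sections 4, 4.1, 4.2, 4.3 and 5.3 side by side)

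| Step | Event | Relative to randomisation |
|---|---|---|
| 1 | Screening, consent, randomisation | – |
| 2 | Obesity Research Unit baseline: OGTT, fasting lipids, bioimpedance, biopsy, pregnancy test | After |
| 3 | Baseline spectroscopy, MRI, elastography | After |
| 4 | Day 1 clinic visit: switch or continue ART | After |

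Sections 4, 4.1 and 4.3 agree, so this is the planned order and not a slip in one sentence.

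**Is the arm withheld?** Sections 4 and 4.2 say when the allocation is acted on. Neither says when it is disclosed. Disclosure at screening is therefore an inference from silence in an open-label design, not a stated fact.

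**Does anything require early randomisation?** The stratification factors are known equally well on day 1, and the allocation is not used before then.

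**Objectives exposed** (section 2). Those with baselines explicitly measured at steps 2-3 are the primary (spectroscopy) and secondary 1 (MRI, bioimpedance), 2 (elastography), 3 (glucose, insulin, OGTT) and 4 (lipids), which makes 5. Secondary 5 is not counted: it depends partly on stored samples, and hsCRP is not in the list of tests for that visit.

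**Scale of losses before the baseline scan.** Inputs: 45 subjects randomised 1:1 (section 3), so 22 or 23 per arm; 25 per arm and a 10% drop-out rate (section 6). The two totals differ, so both are used.

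- One subject lost: 1/23 = 4.3%, 1/22 = 4.5%, 1/25 = 4.0% of the arm.
- Two lost in one arm: 2/23 = 8.7%, 2/22 = 9.1%, 2/25 = 8.0%.
- If the 10% is applied per arm, it covers 2.3, 2.2 or 2.5 subjects. Two losses then use 2/2.3 = 87%, 2/2.2 = 91% or 2/2.5 = 80% of it before any follow-up loss.

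The numbers lost (0, 1 or 2) are assumptions; the documents give no expected figure.

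**The plan's own sample size, for context.** Take a difference of 9, read the 11% CV as a standard deviation on the same scale, and assume two-sided 5% significance (not stated). The normal approximation gives n = 2 × (1.96 + 0.84)² × (11/9)² = 23.4, so 24 per arm. The t-test version gives 24.45, so 25. On these assumptions the stated 25 + 25 matches the requirement before drop-out (24.45/0.9 = 27.2 per arm with it), which leaves little slack for avoidable losses. The finding does not depend on this figure.

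**The case against.** The strongest reply is that the main harm is inferred. No sentence says subjects are told their arm at screening, and the synopsis, listed as an attachment, is not in the available text. That stands, and it is why the finding says baselines may be taken with the arm known.

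The bias is also likely to be limited. Both arms are on unchanged ART at baseline, and subjects know their arm for 24 weeks in any case. Only the interval from screening to baseline is at issue, and its length is not given. Subjects are advised to keep their usual habits. The primary measure is an instrument-derived signal ratio, and section 4.3 sets acceptance limits for elastography. An elastography operator who knows the arm at week 24 is the larger exposure, and moving randomisation does not address it. All of this stands and limits the size of the concern.

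On eligibility, the screening list in section 4.1 is visibly incomplete: it omits the viral load that section 3 requires at screening. A pregnancy test could be intended there too. But the only timing the plan states for that test is after randomisation. Claustrophobia can be asked about at screening, so intolerance that first appears in the scanner is a loss that could not be foreseen. It still matters whether that loss falls before or after randomisation.

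Finally, randomising first spares subjects an OGTT, blood draws and a biopsy without then being allocated. That is a real trade-off, but the plan does not give it as a reason.

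**Conclusion.** The concern holds. The order of events is explicit and consistent across sections. An exclusion criterion is tested only after allocation, although section 4.1 makes freedom from exclusions a condition of entry. Subjects can also be lost to the primary change score between randomisation and the baseline scan, with no rule for handling them. These two points do not depend on when the arm is disclosed. The further risk, that five objectives have baselines taken with the arm known, rests on the absence of a withholding rule and on the open-label design.

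Neither the bias nor the number of losses can be derived from the documents. For scale, each loss costs one arm 4.0-4.5%. Two in one arm (assumed) would cost 8.0-9.1% and use 80-91% of a 10% drop-out allowance applied per arm. The baselines remain pre-treatment, so this does not invalidate the trial. It is an avoidable weakness that should be corrected; confidence is medium because disclosure is inferred.

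**What to change.** Amend sections 4, 4.1 and 4.3 so that randomisation takes place at the existing day 1 Infectious Diseases Clinic visit. It would follow both baseline visits, with all eligibility results available, including the pregnancy test and completion of the baseline scan.

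This changes protocol wording only: the visits and their order stay the same. The cost is that a few subjects may complete the OGTT, blood draws and fat biopsy without being randomised, and that study drug is allocated on day 1.

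If early randomisation must be kept, three statements are needed:

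- the allocation is concealed from subjects and staff until day 1;
- the pregnancy test is done before randomisation, with sections 3, 4.1, 4.3 and 5.3 reconciled;
- section 6 says how a randomised subject without a baseline scan is handled.

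This fallback avoids doing baseline procedures in subjects who are never allocated. It costs an earlier pregnancy test and a procedure for holding back the allocation, and it does not prevent randomising someone who then cannot complete the baseline scan.

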### 4.1. Screening visit

A screening visit will be performed prior to first study visit in Obesity Research Unit. The screening visit consists of the following procedures:

- A physical examination will be performed and demographic data will be recorded including subject's gender, date of birth, ethnicity, substance use, recent and current alcohol use (AUDIT questionnaire), smoking status, weight, height, BMI, and waist and hip circumferences.
- Medical history and current medical conditions and concomitant treatments will be inquired and recorded.
- Blood pressure and heart rate will be measured.

The subject may enter into the study if all the inclusion criteria and none of the exclusion criteria are met and will be randomized to one of the treatment arms after signing the informed consent (IC). Recording of adverse events (AEs) starts from the time that a study subject signs the IC form. The study subjects will be given a study diary, where they can fill in AEs and possible concomitant treatments during the study. They will be asked to fill a dietary and exercise diary for three days at the study start and at the end of study.

#### 4.2. Clinical follow up visits in Infectious Diseases Clinic (Aurora hospital)

Table 1 lists all study procedures in Aurora hospital, Helsinki.

Clinical follow up	Lab measurements	Other
first visit, day 1	HIV viral load, complete blood count, Creatinine, ALT, AST, CD4 count	According to the randomization, switching of a PI or efavirenz to raltegravir, or continuing with the previous ART.
remote contact by phone 1, week 2	complete blood count, CRP, ALT, Glucose, Creatinine	AEs inquired and reported
remote contact by phone 2, week 8	complete blood count, ALT, AST, Creatinine, HIV viral load	AEs inquired and reported
last visit, week 24	HIV viral load, complete blood count, Creatinine, ALT, AST, CD4 count	AEs inquired and reported

#### 4.3. Study procedures in the Obesity Research Unit and in the Radiology Department

The study protocol includes two visits in the Obesity Research Unit. The first visit will take place after randomization and before the switch of the ART. The second visit will take place after 24 weeks of follow up.

Study subjects are advised to fast 10-12 hours before each visit in the Obesity Research Unit (water is allowed during fasting). Alcohol intake is prohibited from 48 h before each study visit. Smoking is prohibited during the visits. Apart from these restrictions the subjects are advised to keep to their usual exercise and lifestyle habits for the duration of the study.

The visits consist of the following study measurements: Oral glucose tolerance test (OGTT), measurements of liver fat by 1H-spectroscopy, body composition by MRI, hepatic stiffness by transient elastography and calorimetry for measurement of basal metabolic rate. Samples of blood, urine, stool and saliva are collected, ECG and subcutaneous adipose tissue biopsies taken, and health questionnaire filled in.

##### Body composition studies

Body composition (total lean and fat mass) will be analyzed by a non-invasive BioElectrical Impedance Analyzer System.

##### Abdominal subcutaneous and visceral fat (MRI)

A series of T1-weighted trans-axial images for the determination of visceral and subcutaneous fat will be acquired from a region extending from 8 cm above to 8 cm below the 4th and 5th lumbar intervertebral discs (16 slices, field of view 375 x 500 mm^2, slice thickness 10 mm, breath-hold TR/TE 91 ms/5.24 ms). Water signal is suppressed using a frequency selective fat excitation. Visceral and subcutaneous fat volumes will be measured using an image analysis program (SliceOmatic, <http://www.tomovision.com/products/sliceomatic.html>).

##### Intrahepatic fat content (1H Magnetic resonance spectroscopy, MRS)

Single voxel (25x25x25 mm^3) proton spectra from the liver will be acquired using 16 excitations, a body matrix surface coil and a 1.5-tesla magnetic resonance device (Avantofit).

Siemens, Erlangen, Germany). A Point resolved spectroscopy (PRESS) single voxel technique will be applied, with an echo time of 30 ms. Respiratory motion will be triggered using a navigator belt so that repetition time will be kept  $> 3000$  ms. Intensities of water signal ( $S_{\text{water}}$ ) ppm and methylene signal ( $S_{\text{fat}}$ ) representing intracellular triglyceride in the liver, resonating at 4.8 and 1.4 ppm, respectively, will be determined. Effects of T2 relaxation will be corrected for water and fat intensities and hepatic fat percentage will be calculated by dividing  $S_{\text{fat}}$  by the sum of  $S_{\text{fat}}$  and  $S_{\text{water}}$ . Signal ratios will be further converted to mass fractions as previously described (15). This measurement of percent hepatic fat by proton spectroscopy has been validated against the lipid content of liver biopsies in humans (16). MRI and MRS methods involve no ionizing radiation exposure.

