## 2. List of study objectives

Primary objective is:

1. Baseline to 24-week Change in Liver Fat (measured by proton magnetic resonance spectroscopy,  $\Delta \%$ )

Secondary objectives are:

1. Baseline to 24-week Change in Body Composition including subcutaneous and visceral adipose tissue volume (measured by magnetic resonance imaging), total body fat and lean tissue mass (measured by Bioelectrical Impedance Analysis)
2. Baseline to 24-week Change in Liver Stiffness measured by transient elastography (Fibroscan ®)
3. Baseline to 24-week Change in Glucose Metabolism including fasting glucose, insulin, 2-h oral glucose tolerance test
4. Baseline to 24-week Change in Lipid Profile (LDL and HDL cholesterol, Triglyceride)
5. Baseline to 24-week Change in Metabolic and Inflammatory Biomarkers (e.g. high-sensitivity C-reactive protein (hsCRP), adiponectin, etc)
6. To collect subcutaneous adipose tissue samples at baseline and 24 weeks for future gene expression studies
7. To collect stool and saliva samples at baseline and 24 weeks for future microbiome studies
8. To collect safety and tolerability data related to the switch to raltegravir
9. Determination of the fatty liver adipose allele (B-PNPLA3)
10. Determination of basal metabolic rate by indirect calorimetry at screening and at the end of study

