## 6. Data analysis

The data will be analyzed by the investigators and the study group.

All variables of the data will be analyzed after the last subject's last visit, when the data have been declared complete.

The data will be analyzed using IBM SPSS Statistics v. 22. The differences between the groups will be analyzed by using chi-square, Fisher's exact, Mann-Whitney U test and others, as appropriate.

As there are no earlier ART-switch studies using H-Magnetic resonance spectroscopy for the quantification of liver fat, the calculation of the study power is an estimate. In the STERAL study evaluating the effect of switching from efavirenz (EFV) to RAL vs. continuing Efv-based ART, a statistically significant difference in the liver fat content using CAP (controlled attenuated parameter) was shown with a study sample of 19 +18 subjects after 48 weeks (7,3% decrease in the RAL vs. 11,0% increase in the Efv arm, p = 0,019) (11).

The power of this study is calculated with the assumption of liver fat being 4.4-5.0% in this study group at baseline. This estimation is based on our previous results published in 2002, when the median liver fat was 8% with lipodystrophic patients and 3% with non-lipodystrophic patients (17). Hadigan et al reported liver fat content being >5% in 42% of HIV positive subjects (18). As the liver fat content correlates with visceral fat mass, studying overweight or obese patients with at least one metabolic syndrome component includes patients at high risk for elevated liver fat content.

In the power calculation, we have used a coefficient of variation (CV) of H-Magnetic resonance spectroscopy being 11% (17). To detect a 9% difference between study arms with 80% power, a minimum sample size of 25 + 25 subjects with a 10% drop-out rate is needed.

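### In this open-label trial the protocol does not provide for the liver spectra (primary outcome) and MRI fat volumes to be quantified masked to arm and visit; coded reading would be a low-burden improvement

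*Combined protocol and SAP*

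**What the plan says.** **Design and sequence.** Section 4 describes a single-centre, randomized, open-label, parallel trial. Step 1 of its flow chart is "Screening visit, signing of the informed consent and randomization". The baseline MR imaging and spectroscopy at Meilahti hospital is step 3, and the regimen is continued or changed at the Infectious Diseases Clinic in step 4. Section 4.3 gives the same order for the first Obesity Research Unit visit: after randomization, before the switch.

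**Primary outcome.** Section 2 names "Baseline to 24-week Change in Liver Fat", measured by proton spectroscopy. The spectroscopy part of section 4.3 fixes voxel size, number of excitations, echo time, T2 correction, the ratio of fat signal to fat plus water signal, and conversion to a mass fraction. The two signal intensities, "resonating at 4.8 and 1.4 ppm, respectively, will be determined". No reader is named, and neither coding nor masking is mentioned.

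**MRI fat volumes (a secondary objective).** Section 4.3 says: "Visceral and subcutaneous fat volumes will be measured using an image analysis program". The software is named. The reader, the degree of operator input and any masking are not.

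**Timing of analysis.** Section 6 places analysis after the last subject's last visit, "when the data have been declared complete". This governs when analysis starts, not what a reader knows.

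**The concern.** Where treatment cannot be masked, masked outcome assessment is the main protection left against detection bias. Stored spectra and images lend themselves to it, because they can be coded before anyone quantifies them.

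The study hypothesis in section 1 is directional: raltegravir might improve liver fat. A reader who knows the arm and the visit could, without intending to, resolve borderline choices in the expected direction. Such choices might include baseline and peak fitting in a spectrum, acceptance of a poor spectrum, or the boundary between visceral and subcutaneous fat. The primary outcome is a change, so the baseline and the week-24 readings both matter.

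**Working it through.** No figure in the plan is in dispute, and masked reading does not alter the sample size. The check is a reading of the text, a short piece of algebra showing which reading shifts matter, and a count of the work.

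**1. Does the allocation exist when scans are quantified?**

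| Step (section 4 flow chart) | Event | Allocation exists? |
|---|---|---|
| 1 | Screening, consent, randomization | Created here |
| 3 | Baseline MR scan | Yes |
| 4 | Regimen continued or switched | Yes |
| 6 | Week-24 MR scan | Yes |

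So it exists for both scans. This shows that arm-aware reading is possible at both time points, not that it happens.

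**2. Does the supplied text prevent it?** The spectroscopy, MRI and data analysis texts were read for masking, coding, an independent reader, or withholding of arm or visit. None appears there or elsewhere in the supplied protocol.

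**3. Which reading shifts would bias the comparison?** Let *b* be the mean shift that the reader adds, by arm (R = raltegravir, C = continue) and visit (0, 24). On the absolute scale:

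observed difference in change = true difference + [(b_R,24 − b_R,0) − (b_C,24 − b_C,0)]

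- A shift common to both arms at a visit (b_R = b_C) cancels.
- A shift in one arm that is the same at both visits also cancels.
- Only a shift whose change between visits differs by arm biases the result.

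A reader who does not know the arm has no direct basis for producing that last kind. Removing visit and date, and reading in random order, also stops pairs being read against each other and spreads any drift in reading across arms and visits. Both time points need coding, because b_R,0 and b_C,0 enter the expression too.

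**4. How large could the bracketed term be?** The documents give no reader variability, no reading-shift figure and no description of operator input, so no value can be put in.

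**5. Workload, before drop-out.** Each subject has two MR examinations (baseline and week 24), and each MRI series has 16 slices (section 4.3).

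- 45 subjects (section 3): 45 × 2 = 90 spectra and 90 MRI series; 90 × 16 = 1,440 slices.
- 25 + 25 subjects (section 6): 50 × 2 = 100 spectra and 100 MRI series; 100 × 16 = 1,600 slices.

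**The case against.** **This is an argument from silence.** That is largely fair. Scans are done at Meilahti hospital and the switch is made at the Infectious Diseases Clinic, so imaging staff may never hear the allocation. The synopsis is listed as an attachment and was not available for this review. Masking may already be the practice. What stands is that the methods text, where a reader would look for the safeguard, does not provide it.

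**The primary measure leaves little room for discretion.** This also stands in large part. The acquisition settings, T2 correction, ratio and conversion are all prescribed. The risk is probably lower here than for the MRI volumes, although the text does not say that determining the intensities is free of operator input.

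**Stronger readings that the documents do not support.**

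- A reader might infer that unmasked investigators quantify the scans, because section 6 says "The data will be analyzed by the investigators and the study group". That sentence opens a section on statistical analysis and says nothing about who reads spectra or images.
- A reader might infer that randomizing before the baseline scan itself causes bias. The order shows only that the allocation exists. With off-line reading done later, scanning before randomization would not prevent arm-aware reading either.
- A reader might try to size the bias against the planning figures in section 6, namely "To detect a 9% difference between study arms with 80% power" and an "assumption of liver fat being 4.4-5.0% in this study group at baseline". Any such percentage would be arithmetic on a shift chosen by the reviewer. Section 6 also does not say whether the 9% is relative or absolute.

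**Conclusion.** The point holds as a recommended improvement, not as an error or a contradiction. In an open-label trial with a directional hypothesis, the supplied text allows the primary-outcome spectra and the MRI fat volumes to be quantified with knowledge of arm and visit, at both time points. No route by which readers learn the allocation is shown, and the size of any bias cannot be estimated from the documents. The potential is probably greater for the MRI volumes than for the spectroscopy ratio.

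The conclusion assumes that quantification is done off-line on stored data, which the protocol does not state, and that no document outside the supplied text already provides for masking. If masking is already done, the remedy is to write it down.

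Transient elastography is a separate case. It is a live reading by one operator, summarised as a median of ten valid measurements with acceptance limits, and coding cannot reach it. The same applies to voxel placement during the scan.

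**What to change.** Add to section 4.3, for spectroscopy and MRI together:

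> Spectra and MRI series are checked for technical quality at acquisition, so that unusable scans can be repeated. All baseline and week-24 data are then coded by a study-team member who does not quantify them and who holds the code. Arm, date and visit are removed, and the usual reader quantifies the data in random order. Results are locked before they are linked to arm and before the data are declared complete.

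For the live steps that coding cannot cover, add that MR and elastography operators are not told the allocation. They will normally still know the time point, and a reader who also acquired a scan may recognise it, so this reduces assessment bias rather than removing it.

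**Cost.** Coding of 90 to 100 spectra and 90 to 100 MRI series, and a quantification stage that may slightly delay the point at which the data are declared complete. It needs no added visit, patient procedure or extra reader, and no change in sample size. Staff time cannot be priced here, because the budget is a separate sheet (section 7).
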